ⁿ PK urine samples, except for the food and gender effect cohorts, will be collected for each specified time interval: pre-dose and between 0-4, 4-8, 8-12, 12-24, 24-48, and 48-72 hours post-dose following the single dose administration (Section 10.3.2). The urine volume at each interval should be recorded as part of PK data.

^o PGX samples (whole blood) will only be collected from the subjects who consented for DNA testing.

^p Details regarding study drug administration are provided in Section 9.3.

BMI: body mass index; ECG: electrocardiogram; FSH: following-stimulating hormone; FU: Follow-up; HbsAg: hepatitis B surface antigen; HCV Ab: hepatitis C antibody; HDL: high density lipoprotein; HIV Ab: human immunodeficiency virus antibody; ICF: informed consent form; LDL: low density lipoprotein; PK: pharmacokinetic(s); PGX: pharmacogenomic(s).

Table 2: Schedule of Assessments - Part B (Multiple Dose Administration)

Assessment	Screening	Admission	Confinement															Follow-up (14 – 16 days after final dosing day)		
	Study Day																			
Assessment	-28 to -2	-1	1	2	3	4	5	6	7	8	9	10	11	12	13	14	15	16	17	28 to 30
Admission ^a		X																		
Randomization			X																	
Confinement		X	X	X	X	X	X	X	X	X	X	X	X	X	X	X	X	X	X	
Discharge ^b																				X
Outpatient Visit	X																			X
Informed Consent ^c	X																			
Inclusion and Exclusion Criteria Check	X	X																		
Demographics	X																			
Medical History	X																			
Smoking Screen (cotinine urine test)	X	X																		
Drugs of Abuse (urine)/Alcohol Screen (urine and breath) ^d	X	X																		

Assessment	Screening	Admission	Confinement																Follow-up (14 – 16 days after final dosing day)		
	Study Day																				
Assessment	-28 to -2	-1	1	2	3	4	5	6	7	8	9	10	11	12	13	14	15	16	17	28 to 30	
Physical Examination ^e	X ^e	X																	X	X	
Prior and Concomitant Medication	Details for all medications will be taken on an ongoing basis from screening to follow-up (FU).																				
Height, Weight, and BMI ^f	X																			X ^f	
Vital Signs ^g	X	X	X ^g	X	X	X															
Peak Expiratory Flow Rate ^h		X	X ^h	X														X ^h	X		X
Safety Single 12-lead ECG	X	X																	X	X	X
Extensive Triplicate ECG ⁱ			X ⁱ	X	X	X	X	X	X	X	X	X	X	X	X	X	X ⁱ	X			
Serology Tests (HBsAg, HCV Ab, HIVAg and Ab)	X																				
Hematology, Coagulation, and Clinical Chemistry ^j	X	X			X				X								X		X		X

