Assessment	Screening	Admission	Confinement																Follow-up (14 – 16 days after final dosing day)	
	Study Day																			
Assessment	-28 to -2	-1	1	2	3	4	5	6	7	8	9	10	11	12	13	14	15	16	17	28 to 30
Urinalysis ^j	X	X			X					X							X		X	X
Alpha-1-acid Glycoprotein	X																			
Total, LDL, and HDL Cholesterol	X																X		X	
C-SSRS	X																X			X
PK Sampling – Plasma ^k			X ^k	X	X	X	X	X	X ^k	X	X	X	X	X	X	X ^k	X ^k	X ^k	X	
PGX Sampling – Whole blood ^l		X																		
Study Drug Dosing ^m			X	X	X	X	X	X	X	X	X	X	X	X	X					
Adverse Event Assessment and Reporting	Ongoing from the time of signing the Informed Consent Form (Non-treatment and Treatment emergent adverse events)																			

^a Subjects will be admitted to the clinic the day prior to study drug administration.

^b Subjects will be discharged on Study Day 17, after the 72-hour PK sample from the final dose has been collected and the final assessment has been completed.

^c At screening, a separate informed consent form (ICF) will be used to obtain the subject's consent for the utilization of their DNA for pharmacogenomic (PGX) testing.

^d For drugs of abuse/alcohol screen, refer to Section 10.6.2. At the time of signing the ICF, a negative result from the breath alcohol test is required.

^e Complete physical examination should be performed at screening only. Abbreviated physical examination should be performed at all other marked study days. See Section 10.6.3.

^f Height and weight will be collected, and BMI calculated at screening. Only weight will be collected at FU.

^g Highlighted time points for vital signs (Section 10.6.3) as follows: pre-dose (baseline), 1, 2, 3, 4, 6, 8, and 12 hours post-dose on Day 1; pre-dose, and at 2, 6, and 8 hours post-dose on Days 2 through 14. Vital signs should be assessed at all other marked study days.

^h Peak expiratory flow rate will be assessed at admission (Day -1), pre-dose (baseline), 2 and 24 hours post-dose after the first dose (Day 1 dosing) and the last dose (Day 14 dosing), and FU.

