In a GLP 28-day repeat-dose study toxicity and TK study, male and female rats were administered 0, 15, 30, or 40 mg/kg/day SKL24741. No unscheduled mortalities were observed. Clinical observations were dose-responsive and included transient ataxia and hypoactivity for both sexes administered \geq 30 mg/kg/day and low body carriage for animals administered 40 mg/kg/day. Isolated incidences of hunched appearance and lateral recumbency were also observed at 40 mg/kg/day. Clinical signs were considered adverse at 40 mg/kg/day due to the nature and severity of the observations. Dose-dependent decrease in body weight, correlating with decreased food consumption, was observed at \geq 30 mg/kg/day; however, these observations were not considered adverse due to their transient nature and reversibility. Clinical chemistry changes included mild, reversible, higher cholesterol concentration in males and females administered \geq 15 mg/kg/day and \geq 30 mg/kg/day, respectively, which were not considered adverse. SKL24741-related increased liver weights were observed in males administered \geq 30 mg/kg/day and females administered \geq 15 mg/kg/day. Microscopic liver findings of minimal centrilobular hepatocyte hypertrophy were observed in males and females administered \geq 30 mg/kg/day. These findings were consistent with potential microsomal enzyme induction in the liver, an adaptive response, and were considered non-adverse due to their minimal severity and partial recovery following the 2-week recovery phase. Based on FDA recommendation, a NOAEL of 15 mg/kg/day was considered for calculating the starting dose (mean combined sex C_{max} values was 3.32 µg/mL and AUC_{24hr} 61.2 µg*h/mL).

In a non-GLP toxicity study, male and female dogs were administered a single dose of 20, 60, 100, or 300 mg/kg SKL24741. At doses \geq 100 mg/kg, clinical signs of lateral (only 300 mg/kg female) and sternal recumbency, ataxia, hypoactivity, emesis, and/or foamy white vomitus, and excessive salivation were observed. Decreased food consumption was noted in animals administered \geq 60 mg/kg with full recovery before the next dosing occasion. The MTD following single oral administration in dogs was 100 mg/kg.

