Based on these data from the most sensitive species (rat), the MRSD is approximately 14.5 mg with a 10-fold safety factor applied to the HED (HED ÷ 10). However, a larger safety factor of approximately 15 was applied to the HED (HED ÷ 15) due to steep dose-toxicity profile in rats and dogs (Section 4.1.1). Therefore, the starting dose of this FIH clinical study will be a single oral dose of 10 mg of SKL24741. With this starting dose, a safety factor would be approximately 33 from the HED derived from the dog.

The first cohort of the single ascending dose (SAD) study will receive a single dose at the Dose 1 level (i.e., 10 mg) and subsequent cohorts will receive doses up to 1000 mg (as a single dose) based on the prediction from allometric scaling and in silico assessment.

However, dose levels of SKL24741 will be adjusted if needed based on plasma exposure, safety and tolerability observed at each dose level during the study.

The single-dose escalation scheme (Part A) is designed to explore a range of doses up to the plasma exposure observed at the NOAEL of 10 mg/kg/day in dogs (Day 28 mean combined sex C_{max} and AUC values of 2.61 µg/mL and 21.7 µg*hr/mL, respectively; **Table 3**) if the safety and tolerability allow reaching this plasma exposure. A few additional single dose levels beyond the dog NOAEL exposures may be considered if the safety and tolerability warrant a higher dose of SKL24741. However, the dose escalation increment will not exceed 1.5-fold between each dose level due to the steep dose response observed in toxicology species (Section 4.1.1). The institutional review board (IRB) will be notified prior to initiating these additional cohorts. In any case, the plasma exposure in humans will not

exceed the exposure observed at the NOAEL of 15 mg/kg/day in rats (Day 28 mean combined sex C_{max} and AUC values of 3.32 $\mu\text{g}/\text{mL}$ and 61.2 $\mu\text{g}^*\text{hr}/\text{mL}$, respectively).

After the first dose level, if drug exposure in humans differ from what is expected from nonclinical studies, the dose-escalation scheme may be re-evaluated. The dose level selected to assess the preliminary food and gender effects may also be re-evaluated. Any changes to the dose escalation scheme will be reviewed and approved by the Sponsor and submitted to the IRB.

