Oxycodone
Phencyclidine
Propoxyphene
Cannabinoid (THC)
MDMA (Ecstasy)
Methaqualone
Ethanol (Alcohol) (Both urine and breath tests)
Tricyclic Antidepressant (TCA)

Other Assessments

Alpha-1-acid glycoprotein
Total cholesterol
LDL cholesterol
HDL cholesterol

^a Postmenopausal status for females of non-childbearing potential will be further confirmed with follicle-stimulating hormone (FSH) serum levels that are consistent with postmenopausal status. Refer to Inclusion Criteria for details (Section 8.1).

ALT: alkaline transaminase; aPTT: activated partial thromboplastin time; AST aspartate transaminase; Gamma-GT: glutamyl transpeptidase; FSH, follicle-stimulating hormone (FSH); HbsAg: hepatitis B surface

antigen; HCV Ab: hepatitis C antibody; HDL: high density lipoprotein; HIV Ab: human immunodeficiency virus antibody; LDH: Lactic dehydrogenase; LDL: low density lipoprotein; MCH: mean corpuscular hemoglobin; MCHC: mean corpuscular hemoglobin concentration; MCV: mean corpuscular volume; PT: prothrombin time; PT INR: PT international normalized ratio; RBC: red blood cell; TCA: tricyclic antidepressant ; THC: cannabinoid; WBC: white blood cell.

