11.4.4.2. Clinical Laboratory Assessments

All statistical analyses of laboratory values will be performed using International System of Units (SI). Hematology, coagulation, clinical chemistry, urinalysis, and cholesterol panel results will be summarized by dose received and by part of the study at each scheduled time point.

The raw values, changes from baseline, percentage change from baseline (for selected laboratory parameters), shifts from baseline (categorical change from baseline), and clinical abnormalities will be summarized as appropriate. Baseline will be defined in the study SAP. Clinically significant abnormal findings will be reported as adverse events.

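### In Part B, cholesterol is scheduled only at Screening, Day 15 and Day 17, so its baseline is an outpatient value 2 to 28 days old and nothing is scheduled beyond 72 hours after the last dose

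*Protocol*

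**What the plan says.** Table 2 (Protocol, Section 2) has a separate row for "Total, LDL, and HDL Cholesterol". It is marked at Screening (Day -28 to -2), Day 15 and Day 17, and blank at Day -1, on all dosing days and at Follow-up (Day 28 to 30). The urinalysis row is marked at both Day -1 and Follow-up, and so is the row for hematology, coagulation and chemistry. The row "Outpatient Visit" places Screening and Follow-up outside the clinic.

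The chemistry draws do not supply the missing values. Table 10 (Section 10.6.2) lists "Total cholesterol", LDL and HDL under other assessments, not under clinical chemistry.

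Section 11.4.4 includes cholesterol among the safety endpoints. Under Section 11.4.4.2, "cholesterol panel results will be summarized by dose received and by part of the study at each scheduled time point", with changes and shifts from baseline; the definition of baseline is left to the SAP.

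Section 4.1.1.3 reports, from the 28-day rat study, "mild, reversible, higher cholesterol concentration in males and females administered" at least 15 and 30 mg/kg/day respectively, judged not adverse. Section 4.2.2 says that human plasma exposure will not "exceed the exposure observed at the NOAEL of 15 mg/kg/day in rats".

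**The concern.** A change from baseline is only as good as its baseline, and the SAP can choose only among samples that were taken. For cholesterol there is one scheduled pre-dose sample, and it is the outpatient one. Exclusion criteria 4 to 6 and Appendix B require prescription and nonprescription drugs, herbals, supplements and vitamins to stop only 14 days before the first dose, and alcohol only 72 hours before. A subject screened early can therefore give the baseline sample while still using products that must later be stopped.

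The second gap comes after treatment. Reversibility was part of how the rat finding was described, and that study had a 2-week recovery phase. Part B has a visit at a similar distance from the last dose, and cholesterol is left out of it. Part A offers no substitute, because Table 1 schedules cholesterol at screening only. Part B therefore holds every scheduled post-dose cholesterol value in the trial.

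**Working it through.** The plan gives no figure to reproduce here; the check is of the schedule and then of precision.

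**1. Reading the row.** The cholesterol row in the extracted table has 21 cells, as the header does, and maps to Screening, Day 15 and Day 17. The urinalysis row, also 21 cells, maps to Screening, Day -1, Days 3, 8, 15, 17 and Follow-up. Some other rows are displaced in extraction: the discharge mark falls under Follow-up, the dosing row shows 13 marks for 14 doses, and the chemistry row has one cell too many. Days 15 and 17 could therefore be off by a column. The blanks at Day -1 and Follow-up agree with the aligned rows.

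**2. Intervals (no Day 0; last dose on Day 14).**

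| Interval | Days |
|---|---|
| Screening to first dose | 2 to 28 |
| Screening to Day 15 value | 16 to 42 |
| Screening to Day 17 value | 18 to 44 |
| Last dose to Day 15 | 15 - 14 = 1 |
| Last dose to Day 17 | 17 - 14 = 3 (72 h) |
| Last dose to Follow-up (no cholesterol) | 14 to 16 |

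Fourteen days before Day 1 is Day -14, so a screening sample from Day -28 to Day -15 can precede the required washout.

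**3. Precision.** Part B has 4 cohorts of 6 active and 2 placebo: 32 subjects, of whom 4 x 2 = 8 are placebo. Assume a within-subject CV of 5% to 10% (not in the protocol), independent between samples, with no drift.

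- Single baseline, whether Screening or Day -1: SD of change = CV x sqrt(1 + 1) = CV x 1.414, giving 7.1% to 14.1%.
- Mean of Screening and Day -1: SD = CV x sqrt(1 + 1/2) = CV x 1.225, giving 6.1% to 12.2%.
- Ratio: sqrt(1.5/2) = 0.866, about 13% smaller.
- SE of one dose (6) against pooled placebo (8) = SD x sqrt(1/6 + 1/8) = SD x 0.540. This gives 3.8% to 7.6% with a single baseline and 3.3% to 6.6% with the mean of two.

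The 13% comes wholly from averaging two samples. The age of the screening value and any pre-washout effect are not in this model.

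**The case against.** A reader might infer that recovery is never measured, or that Days 15 and 17 are on-drug values. The schedule does not support either reading. Both days follow the last dose, and Day 17 against Day 15 is an off-drug comparison scheduled for every subject. Only the later period is missing.

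The protocol also has other routes to later values. Section 10.6.2 lets the investigator repeat tests in the event of unexplained or unexpected clinically significant results. Such results become adverse events, which Section 12.1.1.2 follows to resolution or, if non-serious and ongoing at the last visit, for up to 30 days. That stands for a clinically significant rise. A mild one, which is what the rats showed, would probably trigger neither. Section 12.1.2 mentions clinical laboratory tests at the end-of-study visit, but in general terms; Section 10.1 refers timing to Tables 1 and 2, and Table 2 leaves cholesterol blank at Follow-up.

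Concurrent placebo subjects share the same confinement, so average drift from an old baseline cancels in the comparison. That stands too, although subject-to-subject differences in drift remain as noise. A Day -1 sample would not remove the effect of clinic meals and restricted activity, since these begin at admission. An outpatient Follow-up value carries its own change of diet and must likewise be read against placebo.

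Finally, the analysis is descriptive (Section 11.4.1) with no formal sample size (Section 11.1), so no planned test turns on these standard errors. That is correct and limits the weight of the point.

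**Conclusion.** The point holds as a low-cost weakness of the schedule, not as a contradiction in the protocol. A named safety endpoint with a foreseeable, mild animal signal has one pre-dose value, 2 to 28 days old and possibly pre-washout, and no scheduled value between 72 hours after the last dose and the end of the study. The SAP cannot repair either gap.

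The schedule conclusion rests on the extracted Table 2, where the exact late days are less certain than the two blanks. The SE figures rest on the assumed CV of 5% to 10%. A reader might infer that a fresher baseline by itself yields the 13% smaller SD. It does not: Day -1 alone leaves the SD at CV x sqrt(2) in this model, and its advantage is that it is recent and follows the washout.

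**What to change.** In Table 2, mark the cholesterol panel at Day -1 and at Follow-up, run on the fasting chemistry samples already drawn at those visits. Define the cholesterol baseline as Day -1, or as the mean of Screening and Day -1. The mean is less noisy but gives half the weight to a sample that may precede washout, so the choice should be stated in advance. Summarise Follow-up by dose against pooled placebo as the 14- to 16-day recovery result.

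The cost is 32 x 2 = 64 additional panels and two marks in one row, with no new visit or venipuncture.

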3. LIST OF ABBREVIATIONS

Abbreviation	Term
5-HT	Serotonin 5-hydroxytryptamine
ADD	After-discharge durations
ADME	Absorption, distribution, metabolism, and excretion
AE	Adverse event
AEDs	Antiepileptic drugs
ALT	Alkaline transaminase
aPTT	Activated partial thromboplastin time
AST	Aspartate transaminase
AR	Accumulation ratio
AUC	Area under the concentration-time curve
AUC _{24hr}	Area under the concentration-time curve from time zero to 24 hours post-dose
AUC _∞	Area under the concentration-time curve from 0 to infinity
AUC _t	Area under the concentration-time curve from 0 to t
AUC _τ	Area under the concentration-time curve over the dosing interval
BA	Bioanalytical
BCRP	Breast cancer resistance protein
BK	Big Potassium
BLQ	Below the limit of quantitation
BMI	Body mass index
BSA	Body surface area
CHO	Chinese hamster ovary
CL	Total clearance
CL/F	Apparent clearance
CL _R	Renal clearance
C _{max}	Maximum concentration
CF	Cystic fibrosis
CFR	Code of Federal Regulations
CNS	Central nervous system
CPAP	Clinical pharmacology analysis plan
CRO	Contract research organization

Abbreviation	Term
CRF	Case report form
CRU	Clinical research unit
C-SSRS	Columbia-Suicide Severity Rating Scale
CSR	Case Study Report
CV	Coefficient of Variation
CYP	Cytochrome P450
DMCM	Methyl 6,7-dimethoxy-4-ethyl- β -carboline-3-carboxylate hydrochloride
ECG	Electrocardiogram
eCRF	Electronic case report form
ED ₅₀	Half-maximal effective dose
EDC	Electronic data capture
EDTA	Ethylenediaminetetraacetic acid
EEG	Electroencephalography
EMA	European Medicines Agency
EOS	End of Study
FDA	Food and Drug Administration
FSH	Follicle-stimulating hormone
FIH	First-in-human
f _e	Fraction of drug dose excreted in urine
F _{rel}	Relative bioavailability
FU	Follow-up
GABA	Gamma-aminobutyric acid
Gamma-GT	Glutamyl transpeptidase
GCP	Good Clinical Practice
GI	Gastrointestinal
GLP	Good Laboratory Practice
GMS	Generalized myoclonic seizures
GTCS	Generalized tonic-clonic seizures
HBsAg	Hepatitis B surface antigen
HCN	Hyperpolarization-activated cAMP-regulated cation
HCV	Hepatitis C virus

Abbreviation	Term
HCV Ab	Hepatitis C antibody
HDL	High density lipoprotein
HED	Human equivalent dose
HEK	Human embryonic kidney
hERG	Human ether-à-go-go related gene
HIPAA	Health Insurance Portability and Accountability Act of 1996
HIV Ab	Human immunodeficiency virus antibody
HIV Ag	Human immunodeficiency virus antigen
hNav	Human voltage-gated sodium channels
hDAT	Human dopamine transporter
hNET	Human norepinephrine transporter
HR	Heart rate
IC ₅₀	Half-maximal inhibitory concentration
ICF	Informed consent form
ICH	International Conference on Harmonization
IND	Investigational New Drug (application)
INR	International normalized ratio
IP	Intraperitoneal
IRB	Institutional Review Board
IV	Intravenous
K ₂ EDTA	Di-potassium ethylenediaminetetraacetic acid
LC-MS/MS	Liquid chromatography-tandem mass spectrometry
LDH	Lactic dehydrogenase
LDL	Low density lipoprotein
LMA	Locomotor activity
MAD	Multiple ascending dose(s)
MCH	Mean corpuscular hemoglobin
MCHC	Mean corpuscular hemoglobin concentration
MCV	Mean corpuscular volume
MedDRA	Medical Dictionary for Regulatory Activities
MES	Maximal electroshock seizure

Abbreviation	Term
MRSD	Maximum recommended starting dose
MTD	Maximum tolerated dose
Nav	Voltage-gated sodium channels
NCA	Non-compartmental analysis
NMDA	N-methyl-D-aspartate
NOAEL	No observed adverse effect level
NOEL	No observed effect level
NTD ₅₀	Median neurotoxic dose
PBR	Peripheral benzodiazepine receptor
PEFR	Peak expiratory flow rate
P-gp	P-glycoprotein
PGX	Pharmacogenomic(s)
PK	Pharmacokinetic(s)
PT	Prothrombin time; Preferred Term
PT INR	Prothrombin time (PT) international normalized ratio (INR)
PTZ	Pentylenetetrazol
QA	Quality assurance
QC	Quality control
R _{acc}	Accumulation ratio
RBC	Red blood cell
rPOS	Refractory partial-onset seizures
SAD	Single ascending dose(s)
SAE	Serious adverse event
SaO ₂	Arterial oxygen saturation
SAP	Statistical analysis plan
SAR	Suspected adverse reaction
SD	Standard deviation
SEM	Standard error of the mean
SI	International System of Units
SKLSI	SK Life Science, Inc.
SOC	System Organ Class

Abbreviation	Term
SOP	Standard operating procedure
SRS	Spontaneous recurrent seizures
τ	Dosing interval
$t_{1/2}$	Half-life
TCA	Tricyclic antidepressant
t_{max}	Time to maximum concentration
TK	Toxicokinetic(s)
US	United States
V_d/F	Apparent volume of distribution
WBC	White blood cell
WHO-DD	World Health Organization-Drug Dictionary

4. INTRODUCTION

4.1. Background

Epilepsy is a neurological disorder that is characterized by an enduring predisposition to generate epileptic seizures and the associated cognitive, psychological and social consequences (Fisher et al., 2014). An epileptic seizure has a transient behavioral change that might be objective signs or subjective symptoms (such as loss of awareness, stiffening, jerking, a sensation that rises from the abdomen to the chest, a smell of burnt rubber or *déjà vu*), caused by abnormal excessive or synchronous neuronal activity in the brain (Devinsky et al., 2018). Epilepsy is one of the most common neurologic conditions. Almost 10% of people will experience a seizure during their lifetime (Hauser and Beghi, 2008). Epilepsy is the third leading contributor to the global burden of disease for neurological disorders and affects 65 million people worldwide (Ngugi et al., 2010). About one-third of patients have refractory epilepsy (i.e., seizures not controlled by two or more antiepileptic medications or other therapies). Approximately 75% of epilepsy begins during childhood, reflecting the heightened susceptibility of the developing brain to seizures (Stafstrom and Carmant, 2015).

Although the cause of epilepsy in many patients is unknown, seizures can be the result of almost any insult that disturbs brain function. These insults include acquired causes (for example, after stroke or traumatic brain injury), infectious diseases (such as neurocysticercosis), autoimmune diseases, and genetic mutations. To date, over 500 genes associated with epilepsy have been identified (Devinsky et al., 2018).

Epilepsy is classified in terms of epilepsy syndromes and seizure types. The latter is determined by the electroencephalography (EEG) patterns observed when the seizure is occurring and by the clinical seizure characteristics. Examples of seizure types include absence seizures (previously known as petit mal), simple partial seizures (previously known as focal motor or aura), complex partial seizures (previously known as psychomotor or temporal lobe) and generalized tonic-clonic seizures (also known as grand mal) (Meinardi et al., 1985).

Once seizure types are identified, this information determines the epilepsy syndrome in conjunction with information about cause, age of onset, and interictal EEG abnormalities. Epilepsy can be basically classified as idiopathic (no apparent structural injury, probable genetic cause) or symptomatic (structural brain abnormality of known or unknown cause). Further differentiation can be made on whether the seizures begin in a focal region (partial epilepsy) or begin diffusely (generalized epilepsy). Idiopathic generalized epilepsy is the most common childhood epilepsy; absence, myoclonic, and generalized tonic-clonic seizures may also be seen. In adults, symptomatic partial epilepsy is most common and may cause simple partial, complex partial, or generalized tonic-clonic seizures (Commission on Classification and Terminology of the International League Against Epilepsy, 1981). Although the International League Against Epilepsy updated new classification of epilepsy in 2017, the previous classification method was used to avoid confusion in this summary.

SKL24741 [(1*R*)-2-(5-methyl-1,3,4-oxadiazol-2-yl)-1-[3-[4-(trifluoromethyl)phenyl]phenyl]ethanol] is a novel small molecule that is being developed by SK Life Science, Inc. for the

treatment of epilepsy. SKL24741 is intended for oral administration and is a potent inhibitor of voltage-gated sodium channels (Nav). SKL24741 is a chiral compound with an R-configuration; SKL24741 displays more potent efficacy in a refractory partial-onset seizure (rPOS) animal model and a broader safety margin in animal studies compared to the (S)-enantiomer (SKL24742).

The first-line treatment for epilepsy includes antiepileptic drugs (AEDs) of which over 20 drugs have been approved by the United States Food and Drug Administration (US FDA) and the European Medicines Agency (EMA). However, despite the availability of many AEDs, approximately one-third of patients fail to achieve seizure control ([Devinsky et al., 2018](#)). Therefore, the key unmet needs are: effective drugs for drug-resistant epilepsy, improved tolerability of drug treatment, development of individualized treatments based on epilepsy syndrome, and disease-modifying therapies. Based on the results for SKL24741 in *in vitro* studies and animal models of rPOS and other types of epilepsy, this compound has the potential to address these unmet needs.

Further details regarding the SKL24741 studies are discussed in the [Investigator's Brochure](#).

